15.1 Institutional Review Board (IRB) Approval

Each Investigator must obtain IRB approval prior to the consent of the first Subject; no study-related procedures can occur without the approval and oversight of an IRB.

All Principal Investigators must submit for initial review a copy of the clinical investigational plan (CIP) and a sample Informed Patient Consent Document (IPC) to their institution's IRB. Additionally, patient completed forms (EQ-5D-5L, FJS-12, Hip Evaluation) should be submitted for review. Initial approval must be documented; originals of correspondence and approvals are to be filed by the Investigator and copies forwarded to the Sponsor.

Continuing review and any other additional required submissions will be forwarded for IRB review according to their policies and procedures. Approval or acknowledgement must be documented; originals of correspondence and approvals are to be filed by the Investigator and copies forwarded to the Sponsor.

15.2 Informed Patient Consent (IPC)

The Principal Investigator is responsible for ensuring that no Subject is included in the study without adequate informed consent being provided. Source documents must be maintained, evidencing informed consent was collected prior to participation in the study. Failure to obtain or properly document this process is in violation of the ISO 14155, 21CFR50, the Declaration of Helsinki and this study protocol.

See descriptions of the Informed Consent process in **Section 9**, Informed Patient Consent Process. Each subject is entitled to withdraw from this clinical investigation for any reason without obligation and/or prejudice to further treatment.

The Investigator will clearly document the date and reason(s) for the subject's withdrawal from this clinical investigation, and submit the appropriate form(s) to DePuy Synthes.

15.3 Source Documentation

The Investigator will maintain original source documentation records of each Subject's case history. Case histories include the source worksheets, patient reported outcome measures (PROMs), and medical records, including progress notes, hospital charts, nurses' notes, etc.

Records shall include:

- Documents evidencing informed consent
- All relevant observations concerning adverse events
- Subject history of each Subject upon entering the study
- Information on the condition of the Subject during the course of the study.

15.4 Electronic Case Report Form (eCRF) Completion

Electronic Case Report Forms (eCRFs) in an electronic data collection (EDC) system will be used to collect all Subject data once a Subject is enrolled in the study.

Detailed description of the eCRF components and eCRF completion guidelines are included in the User Instructions available in the MediData Rave System and eCRF Completion Instructions (CCIs), which will be provided to the Investigators and applicable site staff to aid in data entry in the EDC system. The respective eCRFs should be fully completed for each Subject and signed electronically by the Investigator.

15.5 Clinical Investigation Plan (CIP) Adherence

The Investigator must not deviate from the investigational plan. The Investigator will notify the Sponsor, and the reviewing IRB as applicable of any deviation from the investigational plan. The Sponsor will evaluate non-compliance with the CIP to determine appropriate corrective action(s), if applicable. If compliance cannot be secured, the continued non-compliance could result in site suspension or termination.

15.6 Clinical Investigation Plan (CIP) Amendments

Applicable IRB approvals will be obtained prior to implementation of changes in the Clinical Investigational Plan that may affect the scientific soundness of the investigation or the rights, safety or welfare of study subjects. Administrative changes must also be submitted to the reviewing IRB.

15.7 Investigator Reporting Responsibilities

The Principal Investigator is responsible for submitting complete, accurate and timely reports as described below:

Principal Investigator Reporting Responsibilities

Report	Description		
Withdrawal of IRB Approval	The Investigator will notify the Sponsor of a withdrawal of approval by the reviewing IRB of the Investigator's part in an investigation within 5 working days.		
Reports of Deviations from the Clinical Investigational Plan (CIP)	Investigator or delegate will report deviations from the CIP to the Sponsor via the EDC system, and to the reviewing IRB (as applicable per the IRB requirements).		
Other	The Investigator will, upon request by a reviewing IRB, provide accurate, complete, and current information about any aspect of the investigation.		
Serious Adverse Event (SAE defined in Section 8.1)	The Investigator will notify the Sponsor, and their reviewing IRBs as applicable, of all SAEs upon awareness of the event (see section 8.5 for reporting timelines)		
All other Adverse Events (see Section 8 for more detail)	The investigator will submit AEs upon awareness of the event (see section 8.5 for reporting timelines)		

Table 15-1 Principal Investigator Reporting Responsibilities

15.8 Investigator Site Files (ISF or Regulatory Binder)

Each Investigator must maintain accurate, complete, and current information about all aspects of this clinical investigation. This includes documentation relating to the Investigator's participation, Subject information (as applicable), and all correspondence relating to the clinical investigation. Correspondence consists of, but is not limited to, written and verbal correspondence with other participating Investigators, the reviewing IRB, and the Sponsor.

The Investigator will maintain all records relating to the clinical investigation for a minimum period of 2 years after the clinical investigation is completed.

16 Sponsor Obligations

16.1 IRB Approval

Each Investigator must obtain IRB approval prior to consent of the first Subject. Each Investigator must also maintain continuous approval. Documentation of initial approval, subsequent renewals and IRB closure must be provided to the Sponsor and filed on site in the Investigator Site File (ISF). Additionally, amendments to the protocol will be submitted for review before implementation, and copies of the submissions and approvals provided to the Sponsor.

The Sponsor will maintain copies of all site IRB documentation in the Trial Master File.

16.2 Investigator Training, Site Initiation Visit

Prior to enrolling Subjects in this study, the Investigator and/or appropriate Site personnel will be trained in general aspects of study administration, content and manner of administration of the Subject questionnaires, all procedures in the protocol, and the procedure for electronic data acquisition and radiographic transmission.

Training will be done through a combination of teleconferences, Web-Ex conferences and on-site training as appropriate.

16.3 Sponsor Reporting Responsibilities

The devices utilized in this study are not investigational and therefore reporting to regulatory agencies is not required.

Additional reports the Sponsor is responsible for preparing and submitting are described below:

Table 16-1 Sponsor Reporting Responsibilities

Sponsor Reporting Responsibilities		
Report	Description	
Withdrawal of IRB approval	The Sponsor shall notify all reviewing IRBs and participating Investigators of any withdrawal of approval of the investigation by a reviewing IRB within 5 working days after receipt of notice.	
Other	The Sponsor will, upon request by a reviewing IRB provide accurate, complete, and current information about any aspect of the investigation.	

16.4 Study Monitoring

Sponsor oversight will be maintained per Sponsor policies and procedures. Monitoring procedures and frequency will be conducted throughout the course of the study according to the Clinical Monitoring Plan. Qualified site study personnel are expected to meet with the clinical monitor to resolve queries and review action items at any onsite monitoring visit.

During the visit, the Sponsor and authorized Sponsor representatives shall be given access to all study records, to include study Subject medical records.

16.5 Sponsor Study Termination

The Sponsor may prematurely terminate or suspend the clinical study as a whole or at an individual investigational site for significant and documented reasons. Reasons for premature termination or suspension include, but are not limited to safety, inadequate recruitment, Principal Investigator issues, device related problems, alignment with business strategy, or administrative issues.

If suspicion of an unacceptable risk to Subjects arises during the clinical study, or when instructed by an IRB or a Regulatory Authority, the Sponsor shall suspend the clinical study at all active sites while the risk is assessed. The Sponsor shall terminate the clinical study if an unacceptable risk is confirmed, or resume the clinical study following appropriate communication and approval from the IRB and a Regulatory Authority as required.

In terminating the clinical study, the Sponsor and the Principal Investigator will assure that adequate consideration is given to the protection of the subjects' interests. All documentation is archived and the appropriate bodies such as the IRB and any Regulatory Authorities are informed as appropriate.

17 Publication Plan

All manuscripts containing data obtained from this clinical investigation will be reviewed and approved by the Sponsor, and each author, prior to any submission. The current and applicable Johnson & Johnson Medical Device & Diagnostic (MD&D) Publication Policy (J&J Publication Policy) will be followed. Publication will also be managed in accordance with applicable laws and regulations.

DePuy Synthes will require a written agreement for any external author(s) prior to initiating any publication. All authors must disclose financial or personal affiliations that could be considered a conflict of interest.

18 Study Summary Statement

This post-market randomized, controlled, multicenter study has been developed to compare the Anterior Advantage Approach with and without use of KINCISE. Data will be collected from the preoperative, operative, and 6-week and 24-week postoperative time points.

EXHIBIT A – Anticipated Adverse Events

In addition to the information provided in the Instructions for Use included with the packaging for all implants, the following adverse events are anticipated. Assuming the following events are consistent with the normal postoperative course and do not meet the criteria of "serious", then they do NOT have to be reported as Adverse Events.

	Up to 24 Hours Postoperative
Genitourinary	Urinary retention
	Hypotension, not requiring treatment
Cardiovascular	 Hypertension, not requiring treatment
	 Dysrhythmia (resolving within 36 hrs post-op)
Central Nervous	Incisional pain
System	 Post-op consequences of narcotics use
System	Fatigue
	Surgical site ecchymosis
Integumentary	 Sanguinous / sero-sanguinous drainage from incision
integanientary	• Venous congestion without thrombosis (foot swelling alleviated when lower
	limb is raised)
Constitutional	 Elevated temperature (no greater than 101°F)
	Prior to Discharge
	Changes in lab values not resulting in clinical symptomatology (Electrolytes, CBC,
Haematological	BS, PT/ PTT)
	Anemia, not requiring treatment
	Transitory:
	 Nausea
Gastrointestinal	 Vomiting
	 Constipation
	o Diarrhea
	Headache
Central Nervous	Disorientation
System	Confusion
	Dizziness
	Incisional /operative site pain
Respiratory	Atelectasis not requiring treatment
	Foot Swelling not requiring intervention
	Surgical site ecchymosis
Integumentary	Sanguinous / sero-sanguinous drainage from incision
	Skin blisters secondary to tape
	 Suture granuloma not involving cellulitis or deeper infection ("spitting suture",
	abscess suture)
Constitutional	Elevated temperature (no greater than 101°F)

If you have any questions about potential adverse events or adverse event reporting, then please contact DePuy Clinical Research.

EXIBIT B – DEVICE PRODUCT CODES

	0			···	···
100 Series POROCOAT Coating	100 Series GRIPTION® Porous Coating	100 Series DUOFIX® HA Coating	Sector POROCOAT Coating	Sector GRIPTION Coating	Sector DUOFIX Coating
N/A	1217-31-044	N/A	N/A	N/A	N/A
N/A	1217-31-046	N/A	N/A	N/A	N/A
1217-01-048	1217-31-048	1217-11-048	1217-22-048	1217-32-048	1217-12-048
1217-01-050	1217-31-050	1217-11-050	1217-22-050	1217-32-050	1217-12-050
1217-01-052	1217-31-052	1217-11-052	1217-22-052	1217-32-052	1217-12-052
1217-01-054	1217-31-054	1217-11-054	1217-22-054	1217-32-054	1217-12-054
1217-01-056	1217-31-056	1217-11-056	1217-22-056	1217-32-056	1217-12-056
1217-01-058	1217-31-058	1217-11-058	1217-22-058	1217-32-058	1217-12-058
1217-01-060	1217-31-060	1217-11-060	1217-22-060	1217-32-060	1217-12-060
1217-01-062	1217-31-062	1217-11-062	1217-22-062	1217-32-062	1217-12-062
1217-01-064	1217-31-064	1217-11-064	1217-22-064	1217-32-064	1217-12-064
1217-01-066	1217-31-066	1217-11-066	1217-22-066	1217-32-066	1217-12-066
	100 Series POROCOAT Coating N/A N/A 1217-01-048 1217-01-050 1217-01-054 1217-01-054 1217-01-056 1217-01-058 1217-01-060 1217-01-062 1217-01-064 1217-01-066	100 Series POROCOAT Coating 100 Series GRIPTION* Porous Coating N/A 1217-31-044 N/A 1217-31-044 N/A 1217-31-044 1217-01-048 1217-31-048 1217-01-050 1217-31-050 1217-01-052 1217-31-052 1217-01-054 1217-31-054 1217-01-056 1217-31-056 1217-01-058 1217-31-058 1217-01-060 1217-31-060 1217-01-062 1217-31-062 1217-01-064 1217-31-064 1217-01-066 1217-31-064	100 Series POROCOAT Coating 100 Series GRIPTION® Porous Coating 100 Series DUOFIX® HA Coating N/A 1217-31-044 N/A N/A 1217-31-046 N/A 1217-01-048 1217-31-048 1217-11-048 1217-01-050 1217-31-050 1217-11-050 1217-01-052 1217-31-052 1217-11-052 1217-01-054 1217-31-054 1217-11-054 1217-01-055 1217-31-056 1217-11-056 1217-01-058 1217-31-058 1217-11-058 1217-01-060 1217-31-060 1217-11-060 1217-01-062 1217-31-062 1217-11-062 1217-01-064 1217-31-062 1217-11-062 1217-01-064 1217-31-064 1217-11-064 1217-01-066 1217-31-066 1217-11-064	IOO Series POROCOAT Coating IOO Series GRIPTION® Porous Coating IOO Series DUOFIX® HA Coating Sector POROCOAT Coating N/A 1217-31-044 N/A N/A N/A 1217-31-044 N/A N/A N/A 1217-31-046 N/A N/A 1217-01-048 1217-31-048 1217-11-048 1217-22-048 1217-01-050 1217-31-050 1217-11-050 1217-22-050 1217-01-052 1217-31-052 1217-11-052 1217-22-052 1217-01-054 1217-31-054 1217-11-054 1217-22-054 1217-01-056 1217-31-056 1217-11-058 1217-22-058 1217-01-058 1217-31-060 1217-11-058 1217-22-058 1217-01-060 1217-31-062 1217-11-060 1217-22-062 1217-01-064 1217-31-062 1217-11-064 1217-22-062 1217-01-064 1217-31-064 1217-11-064 1217-22-064 1217-01-066 1217-31-066 1217-11-064 1217-22-064	IOO Series POROCOAT CoatingIOO Series GRIPTION* Porous CoatingIOO Series DUOFIX* HA CoatingSector POROCOAT CoatingSector GRIPTION CoatingN/A1217-31-044N/AN/AN/AN/A1217-31-044N/AN/AN/AN/A1217-31-046N/AN/AN/A1217-01-0481217-31-0481217-11-0481217-22-0481217-32-0481217-01-0501217-31-0501217-11-0501217-22-0501217-32-0501217-01-0521217-31-0521217-11-0521217-22-0521217-32-0521217-01-0541217-31-0541217-11-0561217-22-0561217-32-0541217-01-0581217-31-0561217-11-0581217-22-0581217-32-0581217-01-0601217-31-0601217-11-0601217-22-0601217-32-0601217-01-0641217-31-0621217-11-0641217-22-0641217-32-0641217-01-0641217-31-0661217-11-0661217-22-0661217-32-0641217-01-0661217-31-0661217-11-0661217-22-0661217-32-064

Table B-1: Pinnacle Hip System Product Codes

Size	300 Series POROCOAT Coating	Multi-Hole POROCOAT Coating	Multi-Hole GRIPTION Coating
48 mm	1217-03-048	1217-20-048	1217-30-048
50 mm	1217-03-050	1217-20-050	1217-30-050
52 mm	1217-03-052	1217-20-052	1217-30-052
54 mm	1217-03-054	1217-20-054	1217-30-054
56 mm	1217-03-056	1217-20-056	1217-30-056
58 mm	1217-03-058	1217-20-058	1217-30-058
60 mm	1217-03-060	1217-20-060	1217-30-060
62 mm	1217-03-062	1217-20-062	1217-30-062
64 mm	1217-03-064	1217-20-064	1217-30-064
66 mm	1217-03-066	1217-20-066	1217-30-066
68 mm	N/A	1217-20-068	1217-30-068
70 mm	N/A	1217-20-070	1217-30-070
72 mm	N/A	1217-20-072	1217-30-072

Bantam POROCOAT Coating	Bantam GRIPTION Coating
1217-20-038	1217-30-038
1217-20-040	1217-30-040

	Coating	Coating
38mm	1217-20-038	1217-30-038
40mm	1217-20-040	1217-30-040
42mm	1217-20-042	1217-30-042
44 mm	1217-20-044	1217-30-044
46 mm	1217-20-046	1217-30-046

Size

Table B-2: Actis[™] Hip System Product Codes

Standard Offset	Description	Size
101011010	ACTIS COLLARED STD	SIZE 1
101011020	ACTIS COLLARED STD	SIZE 2
101011030	ACTIS COLLARED STD	SIZE 3
101011040	ACTIS COLLARED STD	SIZE 4
101011050	ACTIS COLLARED STD	SIZE 5
101011060	ACTIS COLLARED STD	SIZE 6
101011070	ACTIS COLLARED STD	SIZE 7
101011080	ACTIS COLLARED STD	SIZE 8
101011090	ACTIS COLLARED STD	SIZE 9
101011100	ACTIS COLLARED STD	SIZE 10
101011110	ACTIS COLLARED STD	SIZE 11
101011120	ACTIS COLLARED STD	SIZE 12

High Offset	Description	Size
101012010	ACTIS COLLARED HIGH	SIZE 1
101012020	ACTIS COLLARED HIGH	SIZE 2
101012030	ACTIS COLLARED HIGH	SIZE 3
101012040	ACTIS COLLARED HIGH	SIZE 4
101012050	ACTIS COLLARED HIGH	SIZE 5
101012060	ACTIS COLLARED HIGH	SIZE 6
101012070	ACTIS COLLARED HIGH	SIZE 7
101012080	ACTIS COLLARED HIGH	SIZE 8
101012090	ACTIS COLLARED HIGH	SIZE 9
101012100	ACTIS COLLARED HIGH	SIZE 10
101012110	ACTIS COLLARED HIGH	SIZE 11
101012120	ACTIS COLLARED HIGH	SIZE 12

Table B-3: Corail Hip System Product Codes

Standard C	ollarless (KS)	Standard C	ollared (KA)	High Offset	Collarless	Coxa Vara	Collared
Cat. No.	Size	Cat. No.	Size	(KHO)		(KLA)	
L20106	6*	3L92498	8	Cat. No.	Size	Cat. No.	Size
3L92507	8	3L92499	9	L20309	9	3L93709	9
3L92509	9	3L92500	10	L20310	10	3L93710	10
3L92510	10	3L92501	11	L20311	11	3L93711	11
3L92511	11	3L92502	12	L20312	12	3L93712	12
3L92512	12	3L92503	13	L20313	13	3L93713	13
3L92513	13	3L92504	14	L20314	14	3L93714	14
3L92514	14	3L92505	15	L20315	15	3L93715	15
3L92515	15	3L92506	16	L20316	16	3L93716	16
3L92516	16	3L92508	18	L20318	18	3L93718	18

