8.1 Anticipated Adverse Events / Non-Reportable Adverse Events (to Sponsor ONLY)

There are particular immediate non-serious post-operative events that are changes from the baseline condition of the Subject but are expected events resulting from surgery. For the purposes of this protocol these are referred to as Anticipated Adverse Events and are listed in Exhibit A. If these events occur, they should be recorded in the Subject's medical record, but these should NOT be reported as AEs in the eCRF or to the Sponsor. However, if these events occur with a severity deemed above "expected/normal" or meet the criteria of "serious", they should be reported to the Sponsor by completing an AE eCRF in the study database.

Table 8-1 Definitions of Adverse Event (AE) Types, Device Deficiency		
Adverse Event (AE)	AE is defined as an untoward medical occurrence, unintended disease or injury, or untoward clinical signs (or change or worsening of a pre-existing medical condition) in a patient, which may or may not have an association with the device.	
	All reported AEs (defined in Section 8) will be submitted to the DePuy Synthes Complaint Handling Unit, via electronic reporting from the AE eCRF, who will complete all reporting determinations.	
Serious Adverse Event (SAE)	 SAE is defined as an Adverse Event, regardless of relationship to device or procedure, that: led to a death, 	

Table 8-1 Definitions of Adverse Event (AE) Types, Device Deficiency

	led to a serious deterioration in health that either:		
	 resulted in a life-threatening illness or injury, or 		
	 resulted in a permanent impairment of a body structure or a body function, or 		
	 required inpatient hospitalization or prolongation of existing hospitalization, or 		
	 resulted in medical or surgical intervention to prevent life threatening illness or injury or permanent impairment to a body structure or a body function. 		
	 led to fetal distress, fetal death or a congenital abnormality or birth defect. 		
	• Other serious important medical events. Report when the event does not fit the other outcomes, but the event may jeopardize the patient and may require medical or surgical intervention (treatment) to prevent one of the other outcomes.		

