10.9.4 Secondary Endpoints

All secondary endpoint analyses will be performed on the Per Protocol Population.

Skin-to-skin OR time in minutes will be summarized as a continuous endpoint for both treatments. The difference in means $\mu_I - \mu_C$ will also be summarized as a continuous endpoint. Its 1-sided upper 95% confidence limit and the p-value for the test of non-inferiority with a margin of 3.75 based on a 2-sample t-test will be produced if the alternative hypothesis of non-inferiority of the primary endpoint is rejected.

The difference between acetabular cup abduction angle and plan for each subject will be summarized as a continuous endpoint for both treatments. The proportion of subjects with acetabular cup abduction angle within 10% of plan will be summarized as a categorical endpoint for both treatments. The difference in proportions $P_I - P_C$ will also be summarized as a categorical endpoint. Its 1-sided lower 95% confidence limit and the p-value for the test of non-inferiority with a margin of 10% based upon a normal approximation method will be produced if the alternative hypothesis of non-inferiority of skinto-skin OR time is rejected.

The difference between acetabular cup version angle and plan for each subject will be summarized as a continuous endpoint for both treatments. The proportion of subjects with acetabular cup version angle within 10% of plan will be summarized as a categorical endpoint for both treatments. The difference in proportions $P_I - P_C$ will also be summarized as a categorical endpoint. Its 1-sided lower 95% confidence limit and the p-value for the test of non-inferiority with a margin of 10% based upon a normal approximation method will be produced if the alternative hypothesis of non-inferiority of acetabular cup abduction angle within 10% of plan is rejected.

With no prospectively planned hypotheses, the following secondary endpoints will be summarized at all visits with available data for both treatments as continuous variables:

- The Harris Hip Score (HHS) and change from baseline HHS
- Forgotten Joint Score (FJS) and change from 6-week postoperative FJS
- EQ-5D-5L and change from baseline
- Pain (Groin, Thigh, and Buttock)
- Patient Satisfaction
- Radiographic Outcomes (based upon: AP Hip, AP Pelvis, and Lateral)
- Length of hospital stay after index THA

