8.5 Post-operative details

Post-operative details will be summarized for the subjects in the Safety Analysis Population and for the subjects in the Per Protocol population (both in total and by treatment group):

- Subject taking any narcotic pain medication to manage study hip pain (Y/N);
- Hospital stay less than 24 hours (Y/N);
- Length of hospital stay in days (date of discharge minus date of surgery);
- Location of discharge;
- Narcotics prescribed for pain management (Y/N).

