8.9 Safety Analyses

Adverse Events (AE) will be coded according to the Medical Dictionary for Regulatory Activities (MedDRA) version 22.0. Analyses will be conducted for all subjects in the Safety Analysis Set.

All AEs from the start of device placement until subject finishes participation in the study will be summarized by treatment group and combined with frequencies, number of subjects with at least one AE, and percentages for the following categories:

- Overall
- Device related (AE marked Possible, Probable, or Causal Relationship by investigator)
- Procedure related (AE marked Possible, Probable, or Causal Relationship by investigator)
- Serious (SAE)
 - \circ led to death

The number (%) of subjects with adverse events will be presented by MedDRA system organ class (SOC) and preferred term (PT) for all AEs, and for all SAEs separately for each treatment group and combined. In these summaries, AEs will be sorted by decreasing frequency within each MedDRA SOC and PT in the combined cohort. A subject-level listing will be provided to display details of all reported AEs.

A listing of device deficiencies will also be provided.

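### One block of Exhibit A's reporting exemption ends at each patient's own discharge, so counts of some minor adverse events move with length of stay

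*Protocol*

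**What the plan says.** Protocol 8.1 sets up the exemption: "There are particular immediate non-serious post-operative events that are changes from the baseline condition of the Subject but are expected events resulting from surgery". Such events go in the medical record but not in the eCRF. Exhibit A lists them and states that, if they fit the normal postoperative course and are not serious, "then they do NOT have to be reported as Adverse Events". Section 8.1 also has an override: "if these events occur with a severity deemed above" the expected level, or if they are serious, they are reported.

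Exhibit A has two blocks. The first is headed "Up to 24 Hours Postoperative", the same limit for everyone. The second is headed "Prior to Discharge" and has no hour or day limit.

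Protocol Section 8 makes three kinds of event reportable: device related, procedure related and serious. Reporting starts at first incision. For the analysis, SAP 8.9 states: "All AEs from the start of device placement until subject finishes participation in the study will be summarized by treatment group". The categories include overall and procedure related.

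Protocol 10.9.4 lists "Length of hospital stay after index THA" among the secondary endpoints without a hypothesis, and SAP 8.5 also tabulates stays shorter than 24 hours. Under SAP Section 3, treatment is not blinded once assigned.

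**The concern.** Read by its heading, the second exemption stops when the patient goes home. Take a non-serious headache of ordinary severity on the first postoperative day. In a patient still in hospital it is exempt. In a patient discharged on the day of surgery it is outside the list and reportable if judged device or procedure related. Only the discharge time differs.

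Discharge happens after randomisation and is decided by staff who know the assignment, and length of stay is itself an outcome of the trial. A by-arm AE percentage that includes these terms therefore partly measures discharge timing. If one arm goes home sooner, more of its minor events can be counted with no true safety difference. The pooled percentage likewise depends on discharge practice. Neither protocol 10.9.5 nor SAP 8.9 adjusts for this.

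**Working it through.** The plan states no figure on this point, so there is none to reproduce. The check is a reading of the two blocks, followed by an illustration on assumed inputs.

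**When the exemption ends, by type of term (Exhibit A)**

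| Term | Exemption ends at |
|---|---|
| First block only (e.g. urinary retention, fatigue) | 24 h, same for all |
| Both blocks (surgical site ecchymosis, incisional drainage, incisional pain, temperature up to 101°F) | later of 24 h and own discharge |
| Second block only (e.g. headache, diarrhea, untreated anemia, tape blisters) | own discharge |

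The cut-off varies between patients in the second and third rows. Some assignments are open to judgement. The first block also covers consequences of narcotic use, which could take in nausea, constipation or dizziness, and foot swelling relieved by raising the limb.

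**Assumed inputs (none from the documents)**

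- Incidence I of a listed event in the first days: 20% or 40%.
- Onset uniform over 72 h, or exponential with mean 24 h.
- Every event with onset after the exemption ends is judged related, captured and counted.
- Arm A: 50% discharged at 8 h and 50% at 28 h. Arm B: 30% and 70%.
- True event rates identical in the two arms.

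**Share S(t) of events with onset after time t**

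- Uniform, S(t) = (72 − t)/72: S(8) = 64/72 = 0.889; S(24) = 48/72 = 0.667; S(28) = 44/72 = 0.611; S(52) = 20/72 = 0.278.
- Exponential, S(t) = exp(−t/24): S(8) = 0.7165; S(24) = 0.3679; S(28) = 0.3114; S(52) = 0.1146.

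**Difference between arms**

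Let e be when the exemption ends for a patient discharged at 8 h. The difference is I × (0.50 − 0.30) × [S(e) − S(28)].

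*Second block only, e = 8 h*

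- Uniform: S(8) − S(28) = 0.278. 0.20 × 0.20 × 0.278 = 1.1 points; 0.40 × 0.20 × 0.278 = 2.2 points.
- Exponential: 0.7165 − 0.3114 = 0.4051. 0.20 × 0.20 × 0.4051 = 1.6 points; 0.40 × 0.20 × 0.4051 = 3.2 points.

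*Both blocks, e = 24 h*

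- Uniform: 0.6667 − 0.6111 = 0.0556, giving 0.22 and 0.44 points.
- Exponential: 0.3679 − 0.3114 = 0.0565, giving 0.23 and 0.45 points.

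Each range gives all listed events to one type of term, so the two are not additive.

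**Second model**

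Assume a constant daily rate h of listed, related, non-serious events, counted to day 5. Discharge is on day 1 for 70% of one arm and 50% of the other, and on day 2 for the rest. The difference is 0.20 × [exp(−3h) − exp(−4h)], which is 0.4, 0.8, 1.4 and 2.0 points for h = 0.02, 0.05, 0.10 and 0.20. Nobody leaves before 24 h here, so this applies equally to shared and second-block-only terms. It lies within the overall span above.

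**The case against.** The case against is strong on scope.

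- A reader might infer that AE counting as a whole starts at a different time for each patient. It does not. Reporting starts at first incision and the summary at device placement, for everyone. Serious, above-expected and unlisted events count throughout. Only expected, non-serious terms in the second block have a moving cut-off.
- No passage says outright that these events become reportable after discharge. That follows from the heading, and a non-serious event must still be judged device or procedure related.
- Several terms are also in the 24-hour block, so very early discharge changes nothing for them within the first 24 hours.
- A reader might infer that the arms differ by construction. They do so only if length of stay differs by arm. Randomisation is blocked on site-specific sticker sheets, so site discharge habits alone should not separate the arms.
- Capture after discharge may be poor. Laboratory changes, untreated anemia and atelectasis are unlikely to be found at home, and the six-week visit window opens only at day 14. This shrinks the artefact. It does not reverse the rule's own effect, because an exempt inpatient event counts as zero.
- A reader might infer that the unreported events are lost. Protocol 8.1 requires them in the medical record and 8.3 asks for adverse events to be noted in source documents with relationship ratings. They are missing from the eCRF and hence from the planned tables.
- The AE tables are descriptive and no AE hypothesis is tested.

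All of this stands and limits the point. None of it supplies a common cut-off for the second block, and no other section corrects for its absence.

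**Conclusion.** The point holds in narrow form and is minor. Ascertainment of expected, non-serious second-block events depends on the patient's discharge time. It can distort the descriptive overall and procedure-related AE percentages by arm if stay differs by arm. The primary analysis, the sequentially tested secondary endpoints and the serious-event summaries are not touched.

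The documents do not give the size. On the assumed incidence, onset and discharge patterns it is about 0.2 to 0.5 percentage points if the terms are in both blocks and 1.1 to 3.2 points if they are only in the second. It is lower to the extent that events are judged unrelated, are not captured after discharge, or occur in subjects who already have another counted AE. With equal stay in the two arms it is zero between arms. The documents do not show that stay will differ, so they do not support a claim that the safety comparison is biased, only that the rule leaves it open to bias.

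**What to change.** In Exhibit A, replace the discharge-based heading of the second block with one fixed postoperative time, set by the sponsor and the same for all subjects whether or not they have gone home. The 24-hour block shows that a common clock is workable.

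For data already collected, keep the full AE tables in SAP 8.9 as planned and add one supplementary by-arm table. In it, non-serious Exhibit A terms count only if onset is after a common postoperative day by which nearly all subjects have been discharged. Earlier ones are listed separately. The AE eCRF records onset and SAP 8.5 uses the discharge date, so no new data are needed. This restriction should not be applied to the main tables, because it would remove early events of above-expected severity that protocol 8.1 deliberately makes reportable. No above-expected or serious event should leave the main tables.

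The cost is a one-line change in Exhibit A, a short addition to SAP 8.9 and one extra table. Some mild early events after discharge would no longer be reported.
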